6.4 Follow-Up (48 to 72 hours post-drug administration)

At approximately 48, and 72 ± 8 hours after methadone administration, participants will return to the DEPRU for the following procedures:

- Review of concomitant medications
- Blood collection for PK analysis
- Pupillometry, goggles for dark-adapted pupil diameter
- Vital signs, including RR, end-expired CO₂, HR, BP, and SpO₂
- Observed sedation, MOAA/S
- Thermal pain tolerance threshold
- Subjective self-assessment, VAS
- Safety event assessment

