6.7.4 PK Sampling Schedule

The total number of PK blood samples will be 18, 2 ml/sample, 36 ml (less than one-quarter cup). Blood will be centrifuged and plasma removed and stored at -70°C until shipment to a laboratory for analysis. The time of each sample collection should be recorded.

Table 4. Optimal PK sampling schedule relative to single dose of methadone

PK Time Point Sample Number	Elapsed Time After Dose (hh:mm)	
1	Baseline draw	
2	Start IV dose 0:00 + 0:01 ¹	methadone HCl 0.1 mg/kg bw IV push over 1 -2 minutes (including 3ml 0.9NS flush immediately following study medication administration)
3	0:05 ± 0:01	
4	0:10 ± 0:01	
5	0:15 ± 0:01	
6	0:30 ± 0:05	
7	1:00 ± 0:10	
8	1:30 ± 0:10	
9	2:00 ± 0:10	
10	4:00 ± 0:30 ²	
11	6:00 ± 0:30	
12	12:00 ± 0:30	
13	18:00 ± 0:30	
14	24:00 ± 0:30	

15	30:00 ± 1:00
16	48:00 ± 8:00
17	72:00 ± 8:00
18	96:00 ± 8:00

¹Immediately after starting IV dose

²Food can be served after the 4:00 sample collection.

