7.1.4 Preparation and Administration

Methadone will be prepared by Duke Investigation Drug Services (IDS). Each participant will receive 0.1 mg of methadone per kg of body weight from the 10 mg/mL stock concentration administered via IV push. Methadone (0.1mg/kg bw) will be administered via IV push followed by 3mL flush over 2 minutes. The time IV push begins and the time flush ends will be documented on the source.

Refer to MOP for details.

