11.1 Study Endpoints

11.1.1 Primary Endpoints

The list of primary endpoints includes the following:

- Clearance (CL)
- Volume of distribution (Vz)
- Half-life ($t_{1/2}$)
- Area under the curve (AUC)
- Maximum concentration (C_{max})
- Time to maximum concentration (T_{max})
- Minimum concentration (C_{min})
- Elimination rate constant (k_e)

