11.3 Analysis Plan

Noncompartmental analysis will be conducted to determine methadone PK. Compartmental modeling may be explored. Additional details are in the statistical analysis plan.

Descriptive statistics, such as number of observations, mean, median, standard deviation, standard error, minimum, and maximum, will be presented for continuous variables (such as age, weight, etc.). Other descriptive statistics, such as counts, proportions, and/or percentages, will be presented to summarize discrete variables (such as race, sex, etc.). All descriptive analyses will be presented overall. A 95% confidence level will be used for confidence intervals. A detailed description of statistical methods and secondary analyses will be prepared and presented in the statistical analysis plan prior to data lock for final analyses.

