11.3.1 Primary Analysis

The dosing, sampling, and demographic information recorded on the eCRFs will be merged with bioanalytical information to create a PK dataset for methadone. A noncompartmental PK analysis will be performed in Phoenix WinNonlin (version 6.3 or later) using concentration–time data of methadone in plasma. The PK parameters for methadone will be summarized using descriptive statistics, including arithmetic mean, standard deviation, minimum, median, maximum, and geometric mean.

Following the study dose on Day 0, peak drug concentration (C_{\max}), time at peak concentration (T_{\max}), and area under the concentration versus time curve (AUC) will be calculated using the observed data for methadone as appropriate and, if possible, depending on actual samples collected. AUC will be calculated using the linear trapezoidal method. At least 3 time points after the last dose with measurable plasma concentrations will be required for the calculation of AUC_{0-24} .

In addition, the following additional PK parameters will be estimated as appropriate and, if possible, depending on actual samples collected: apparent terminal elimination rate constant (k_e), terminal-phase disposition half-life ($t_{1/2}$), total clearance (CL), and volume of distribution during terminal phase (V_z). k_e will be determined as the slope of a log-linear least squares of at least 3 concentration–time points after the last dose judged, by visual inspection, to be in the apparent terminal elimination phase. Half-life will be calculated as $t_{1/2} = \ln 2/k_e$.

Nominal sampling time will be used in PK calculations, unless actual times are needed. If samples are below the quantification limit and occur prior to the time at C_{\max} , a value of zero will be assigned; for samples occurring after C_{\max} , half the quantification limit will be assigned for a single below-quantifiable-limit sample, or zero for all values in consecutive samples that are below quantifiable limit.

Compartmental methods will also be explored. Please see the PK analysis plan (PKAP) for additional details.

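### The noncompartmental analysis defaults to nominal times, with no rule for using actual ones, although the 48, 72 and 96 h samples may each be up to 8 h off schedule

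*Combined protocol and SAP*

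**What the plan says.** Section 11.3.1 sets the time basis for the primary analysis: "Nominal sampling time will be used in PK calculations, unless actual times are needed". It names no deviation threshold, sample, parameter or decision-maker for the exception. For ke, it says the constant "will be determined as the slope of a log-linear least squares of at least 3" points, picked by visual inspection as lying in the terminal phase. Half-life follows from ke. Section 11.1.1 lists ke, half-life and Vz among the primary endpoints, and Section 11.3.1 summarises the PK parameters with, among other statistics, SD, minimum and maximum.

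Table 4 in Section 6.7.4 gives windows of ±0:30 at 24 h, ±1:00 at 30 h and ±8:00 at 48, 72 and 96 h. The last three are outpatient returns; Section 6.4 reads "72 ± 8 hours after methadone administration, participants will return to the DEPRU", and Section 6.5 gives the same window for 96 h.

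The raw material for actual times is foreseen. Section 6.7.4 says "The time of each sample collection should be recorded", and Section 7.1.4 says "The time IV push begins and the time flush ends will be documented on the source".

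Further detail is deferred. Section 11.3 says "Additional details are in the statistical analysis plan", and Section 11.3.1 ends "Please see the PK analysis plan (PKAP) for additional details". Neither separate plan was available for this review.

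**The concern.** The samples with the widest windows are the ones that fix the terminal slope. Under the stated default, a sample drawn at 40 h or at 56 h goes into the regression as 48 h. The participant's fitted ke is then wrong by an amount that depends only on when that person came to the clinic, and the error passes to half-life and Vz.

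The analysis is descriptive, so no test or decision threshold is at risk. What is at stake is the individual estimates and their reported spread. Section 2.2 gives understanding variation in drug disposition as part of the rationale, and under the default some of the reported variation would be scheduling. Because *needed* is undefined, two analysts could both follow Section 11.3.1 and report different half-lives. The choice could also be made after the concentrations are known, alongside the visual choice of terminal points.

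**Working it through.** The plan gives no figure of its own on this point, so there is none to reproduce first.

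**Inputs from the documents.** Sampling times and windows (Table 4); at least three terminal points and the linear trapezoidal rule (Section 11.3.1); terminal half-life 8–59 h (Section 2.1.1); CV of CL up to 38% and N = 15 (Section 11.6).

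**Assumptions.** The distribution of arrivals within the window, their correlation between visits, and the shape of the early curve.

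**Formula.** Let d_i be actual minus nominal time. In the log-linear phase, ln C = a − ke·(t_i + d_i). Regressing on the nominal t_i gives

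estimated ke / true ke = 1 + Σ w_i·d_i, with w_i = (t_i − t̄) / Σ(t_i − t̄)².

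The relative error does not depend on ke, and a constant shift of time zero cancels from the slope.

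**Three points (48, 72, 96 h).** The ratio is 1 + (d96 − d48)/48; the middle point has no weight.
- Extreme case: opposing 8 h deviations give 1 ± 16/48, so ke is 1.33 or 0.67 times its true value and half-life is 0.75 or 1.50 times.
- Uniform, independent arrivals: the SD of one deviation is 8/√3 = 4.62 h, so the SD of the ratio is √2 × 4.62/48 = 13.6%.
- An error above 10% needs |d96 − d48| > 4.8 h; its probability is (1 − 4.8/16)² = 49%.

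**Five points (24, 30, 48, 72, 96 h).** The mean is 54 h, the deviations from it are −30, −24, −6, 18 and 42, and their squares sum to 3,600. Late visits contribute (64/3)(36 + 324 + 1,764) = 45,312. The 24 h and 30 h windows contribute 75 + 192 = 267. The SD is √45,579 / 3,600 = 5.9%. With correlation 0.5 between late visits, the late term becomes (64/3)(2,124 + 396) = 53,760, and the SD is √54,027 / 3,600 = 6.5%.

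**SD of the relative error in ke:**

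| Late arrivals | 3 points (48–96 h) | 4 points (30–96 h) | 5 points (24–96 h) |
|---|---|---|---|
| ±8 h, independent | 13.6% | 7.2% | 5.9% |
| ±8 h, correlation 0.5 | 9.6% | 6.6% | 6.5% |
| ±8 h, correlation 0.8 | 6.1% | 6.2% | 6.8% |
| ±4 h, independent | 6.8% | 3.7% | 3.0% |
| ±2 h, independent | 3.4% | 1.9% | 1.5% |

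For 3/4/5 points, simulation puts the share of participants whose ke is off by more than 10% at 49/18/8% (±8 h, independent), 30/12/12% (correlation 0.5) and 11/7/15% (correlation 0.8). The central 95% of half-life ratios, with independent full-window arrivals, is 0.79–1.35 (3 points), 0.88–1.15 (4 points) and 0.90–1.12 (5 points).

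**Every late visit 8 h late.** Five points: 8 × (−6 + 18 + 42)/3,600 = +12%. Four points: 8 × 31.5/2,475 = +10%. Three points: 0. If such lateness were common across participants, it would shift the mean and not only add scatter.

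**Vz and CL.** These were simulated on a noise-free two-compartment curve (assumed distribution half-life 0.5 h, 40% of the initial level in the terminal phase), with AUC extrapolated by C_last/ke, CL = Dose/AUC and Vz = CL/ke, comparing nominal with actual times under independent full-window arrivals. For half-lives of 20–59 h, the SD of the Vz error is 9–15% (3 points), 4–7% (4 points) and 2–5% (5 points); for CL it is 2.5–5.8%. A half-life of 8 h is left out: 96 h is then 12 half-lives, 0.5¹² = 0.02% of the terminal intercept, and no assay limit is given.

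**What barely moves.**
- Mean half-life is biased by 0.4% (5 points) to 2% (3 points).
- An assumed true half-life CV of 40% becomes √(1.16·e^(0.060²) − 1) = 40.5% (5 points) or √(1.16·e^(0.139²) − 1) = 42.7% (3 points).
- For CL at N = 15, the interval is exp(±2.145·√ln(1 + CV²)/√15). With CV 38% it is 82–123%. With √(0.38² + 0.058²) = 38.4% it is 81–123%. Both lie well inside the 60–140% of Section 11.6.

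**The case against.** The text does not require the harmful reading. A sample several hours off schedule is the obvious case for the exception, and a sensible analyst would invoke it. The criterion may stand in the SAP or PK analysis plan. Nothing is lost at collection, so actual times can still be used. The largest figures need a three-point fit, arrivals spread over the whole 16 h and independent visits all at once, while Sections 6.4 and 6.5 aim for approximately the nominal times. Other cases are milder. A seven-point 12–96 h fit with independent full-window arrivals gives an SD of 4.9%, and a three-point fit with visit correlation 0.95 gives about 3%. Against a half-life range of 8–59 h, such scatter is small.

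Most of this is correct, and it limits the size of the point. The effect is conditional, the three-point independent case is an upper case, and the means and CL are safe. It does not remove the point. Section 11.3.1 states its own default, and a different rule in another plan would conflict with it. The three-point fit is expressly allowed. More points or correlated visits do not reliably help: the seven-point fit rises to 6.0–6.6% at correlations of 0.5–0.8. That actual times should be available is a reason to use them.

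**Conclusion.** The concern holds. Section 11.3.1 makes nominal time the default, gives no criterion for leaving it, and so allows deviations of up to 8 h to enter the terminal slope. If the default is applied to the late samples, the added SD in an individual ke is roughly 5–14% with independent full-window arrivals, depending on how many points are fitted. It is 3–7% for 3- to 5-point fits if arrivals keep within ±4 h, and 1.5–3.4% within ±2 h. Half-life is affected to a similar degree. Vz is affected less when the half-life is long or more points are fitted.

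The damage is to individual values, SD, minimum and maximum for three of the eight listed primary endpoints. Under random arrivals, mean half-life and the precision of CL are hardly affected. All sizes rest on assumed arrival patterns, since the documents contain no arrival data, and the separate SAP and PK analysis plan, which were not available, may already prescribe actual times. Given how cheap the remedy is, it should be made before analysis.

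**What to change.** Replace the sentence in Section 11.3.1 with:

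> Actual elapsed time from the recorded start of the IV push will be used for all individual noncompartmental parameters. Nominal time will be used only for summary tables and mean plots, or where an actual time was not recorded; such samples will be flagged in the listing.

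Push start is the natural origin because Table 4 counts from the start of the IV dose. Put the same wording in the PK analysis plan. Check that the push start time, which Section 7.1.4 places on the source, and every sample time are fields in the eCRF and the PK dataset; the text does not expressly say that the dose clock time gets there.

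The cost is one sentence, matching text in the PK analysis plan, the field check and a small programming task. Individual profiles will no longer share one time grid. No samples, visits or participants are added.

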Russell et al. 2013 ²³	75 Adult women - 25 methadone - 50 control	fentanyl, morphine, fentanyl and morphine	Caesarean delivery	The methadone group had lower pain scores and decreased opioid requirements immediately postoperatively, as well as decreased opioid use over 48 hours.
Gottschalk et al. 2011 ²⁴	30 Adults (18 – 75) - 13 methadone	Sufentanil	Spinal fusion	The methadone group had decreased pain scores at 48 hours

	- 16 sufentanil			and decreased opioid usage at 48 hours compared to the sufentanil group .
--	-----------------	--	--	---

Methadone was, however, developed and approved long before the regulatory requirements for pharmacokinetic (PK) and pharmacodynamic (PD) characterizations and numerous *in vitro* and *in vivo* preclinical and clinical studies, which are required today for drug approvals. While some investigations in the past few years have discovered missing information regarding methadone biotransformation, drug interactions, and genetics,²⁵⁻²⁷ much fundamental information about methadone PK and PD remains missing. In addition, far more is known about the pharmacology of oral methadone used in high doses for the treatment of opioid addiction (80-160 mg daily) than about smaller intravenous doses used for acute pain (5-10 mg).

Based on known information, methadone, is clinically used as a racemic mixture, with R-methadone acting on the mu receptor, while both R- and S-methadone act to antagonize N-methyl-D-aspartate receptors.²⁸ The drug is lipophilic and has linear PK with a steady state volume of distribution ranging from 2-6 L/kg. Methadone is also 85-90% protein bound in plasma, primarily to alpha1-acid glycoprotein. Metabolism of methadone primarily occurs via CYP2B6 N-demethylation to inactive metabolites, primarily ethylidene-1,5-dimethyl-3,3-diphenylpyrrolidene (EDDP).²⁵ Methadone has a highly variable clearance, ranging from 3-10 L/h, and a terminal half-life of 8-59 hours. However, methadone persists in the liver and other tissues, with slow release sometimes resulting in prolonged duration of action.²⁹

Because of its potential prolonged duration of action, labeled dosing of intravenous (IV) methadone for use in opioid non-tolerant patients is 2.5-10 mg every 8-12 hours, slowly titrated to effect. Available data on methadone PK during treatment of acute pain are listed in **Table 2**.

Table 2. Methadone PK during treatment of acute pain

Study	Population (age)	Route	Dose	Substrate	Results

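### The terminal-slope fit is not limited to quantifiable concentrations, so a substituted half-LLOQ value at 96 h could distort ke, half-life and Vz

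*Combined protocol and SAP*

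**What the plan says.** Section 11.3.1 (Primary Analysis) sets the rule for samples below the quantification limit (BLQ). Before Cmax they become zero. After Cmax, "half the quantification limit will be assigned for a single below-quantifiable-limit sample". Where two or more in a row fall below the limit, the section instead prescribes "or zero for all values in consecutive samples that are below quantifiable limit".

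The elimination rate constant is the "slope of a log-linear least squares of at least 3 concentration–time points after the last dose judged, by visual inspection", to lie in the terminal phase. Half-life is ln 2/ke. CL and Vz are estimated alongside. On area the section says "AUC will be calculated using the linear trapezoidal method"; it does not describe extrapolation beyond the last sample or define the last usable concentration.

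The AUC0-24 criterion is worded differently: "At least 3 time points after the last dose with measurable plasma concentrations will be required". No such condition is attached to the ke points. Further PK detail is left to a PK analysis plan (PKAP), which is not among the documents.

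Sections 3 and 11.1.1 list CL, Vz, half-life, AUC, Cmax, Tmax, Cmin and ke as the primary endpoints. Table 4 places the last samples at 24, 30, 48, 72 and 96 h. Section 2.1.1 expects "a terminal half-life of 8-59 hours". Section 4.5 names the assay type but gives no lower limit of quantification (LLOQ).

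**The concern.** A single late BLQ sample, most naturally the one at 96 h, becomes a positive number fixed by the assay limit rather than by the participant. Nothing in 11.3.1 keeps that number out of the terminal regression, where as the latest point it has the most leverage. Two analysts could both follow the plan, one including the point and the other dropping it, and report different half-lives for the same participant.

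The participants affected are those who eliminate fastest. Any error would therefore distort the between-participant spread as well as individual values, and section 2.2 gives understanding variation in disposition as a purpose of the study.

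Zeros raise a separate issue. They can alter AUC. If Cmin (not defined further in 11.3.1) is the lowest post-dose value, a zero Cmin makes the geometric mean that 11.3.1 plans to report either zero or undefined.

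**Working it through.** The plan states no figure for this rule, so there is none to reproduce.

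**Set-up (assumed).** Error-free mono-exponential decline; samples at the Table 4 nominal times; only the 96 h sample BLQ, so C96 < LLOQ ≤ C72.

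**Three-point fit (48, 72, 96 h).** The times are equally spaced, so the least-squares slope uses only the end points: ke = ln(C48/C96)/48. Let r = (LLOQ/2)/C96 be the ratio of the substituted to the true 96 h value. With true half-life T,

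estimated half-life = 48 / (48/T − log2 r).

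The LLOQ lies between C96 and C72, so r runs from 0.5 to (C72/C96)/2.

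- T = 8 h: C72/C96 = 2^3 = 8, so r is 0.5 to 4. Half-life is 48/(6+1) = 6.9 h to 48/(6−2) = 12.0 h (−14% to +50%); ke is +17% to −33%.
- T = 12 h: C72/C96 = 2^2 = 4, so r is 0.5 to 2. Half-life is 48/(4+1) = 9.6 h to 48/(4−1) = 16.0 h (−20% to +33%); ke is +25% to −25%.

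**Five-point fit (24, 30, 48, 72, 96 h).** The mean time is 54 h and the sum of squares is 900+576+36+324+1764 = 3600. The 96 h point carries 42/3600 = 0.0117 per log unit, against 24/1152 = 0.0208 in the three-point fit, a ratio of 0.56.

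- T = 8 h: ke error is −0.0117 × ln r / 0.0866, which gives +9% to −19%; half-life 7.3 to 9.8 h.
- T = 12 h: ke error is +14% to −14%; half-life 10.5 to 14.0 h.

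**CL and Vz.** Take CL = Dose/AUCinf, with AUCinf the linear trapezoid plus Clast/ke (this extrapolation is assumed), and Vz = CL/ke. Compare with an analysis that stops at the last quantifiable sample. For half-lives of 8 to 24 h and a three-point fit, CL changes by −1.6% to +5.2%, and Vz by about −30% to +50%.

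**Zeros.** ln(0) is undefined, so zeros cannot be points in the fit. If 72 h and 96 h are both set to zero and the trapezoid runs through them without extrapolation, the area given after 48 h is 24 × C48/2 = 12 × C48, against a true C48/ke. As a share of AUCinf the difference is (12 × ke − 1) × 2^(−48/T):

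- 8 h: (1.04 − 1)/64 = +0.1%
- 12 h: (0.693 − 1)/16 = −1.9%
- 24 h: (0.347 − 1)/4 = −16%

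**Can the rule be triggered?** Section 2.1.1 gives CL 3-10 L/h and a volume of 2-6 L/kg. Assume 70 kg, so the 0.1 mg/kg dose is 7 mg. With 2 L/kg and 10 L/h:

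- V = 140 L and C0 = 7 mg/140 L = 50 ng/mL
- ke = 10/140 = 0.0714 per h, half-life 9.7 h
- C72 = 50 × exp(−5.14) = about 0.3 ng/mL
- C96 = 50 × exp(−6.86) = about 0.05 ng/mL

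For this participant an LLOQ between about 0.05 and 0.3 ng/mL gives a single BLQ at 96 h. A higher limit makes both samples BLQ, so the zero rule applies. A lower one triggers nothing.

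**The case against.** The strongest reply is that the plan never says substituted values are used for ke. Points are chosen by visual inspection, so an analyst may leave one out, and the PKAP may already require it. That is fair: this is an unclosed gap, not an instruction to fit imputed points. But permission to omit a point is not a rule. The section asks for measurable values in its AUC0-24 criterion and does not do so for ke.

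The second reply is that the scenario is narrow. It needs exactly one terminal BLQ, an LLOQ inside a particular interval and, for the larger figures, a fit on only three points. All of this stands. The percentage ranges do not need the LLOQ's value, but whether the case arises at all depends on it.

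A reader might go further and infer three things that the documents do not support:

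- **That the zeros also bias ke.** They cannot enter a log-linear fit.
- **That the error is a bias in one direction.** ke is too high when true C96 exceeds half the LLOQ and too low when it is below. If log LLOQ were uniform between the two concentrations, mean log2 r would be 0.5 at 8 h and 0 at 12 h, giving a mean three-point ke error of −0.5/6 = −8% and 0%.
- **That CL is distorted like half-life, or that the sample size is undermined.** CL moves by a few percent where BLQ is plausible, and section 11.6 bases the sample size on CL estimated by population PK.

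**Conclusion.** The concern holds as a gap with a conditional effect. As written, 11.3.1 allows a lone half-LLOQ value into the terminal regression. If that happens at 96 h in a three-point fit, half-life can come out at 6.9 to 12.0 h for a true 8 h, and 9.6 to 16.0 h for a true 12 h. A five-point fit roughly halves the error. The primary endpoints at risk are ke, half-life and Vz in faster eliminators. CL is little affected, at about −2% to +5% for half-lives up to 24 h. Zeros affect AUC and Cmin only.

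These sizes rest on an error-free mono-exponential profile. The CL and Vz figures also assume extrapolation from the last value, and the trigger example assumes 70 kg. How many participants would be affected cannot be said without the LLOQ. The point is worth correcting because the present rule puts assay-determined numbers into the dataset, while restricting the fit to quantifiable values gives no error in ke in this model.

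**What to change.** In section 11.3.1 and the PKAP, replace the post-Cmax substitution rule:

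- Keep zero for BLQ samples before Cmax.
- Treat BLQ samples after Cmax as missing for the noncompartmental analysis.
- Fit ke on quantifiable concentrations only, still at least three, and report ke and its dependants as not estimable otherwise.
- End AUC at the last quantifiable concentration, or extrapolate from it, and say which.
- State how Cmin is reported when late samples are BLQ, so that no zero enters the geometric mean.

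If the PKAP already restricts the ke fit in this way, align 11.3.1 with it and cite it. The cost is a few sentences and no data. It is best done before any concentrations are seen, with the assay's LLOQ stated at the same time.
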